12.1 Description of efficacy variables

ACR 20/50/70

ACR20 is a binary response variable defined for each subject. A subject will be considered a responder according to ACR20 criteria if he/she has at least (i.e., \geq):

- 20% improvement from baseline in tender 78-joint count
- 20% improvement from baseline in swollen 76-joint count

- 20% improvement from baseline in at least 3 of the following 5 measures:
 - Patient's assessment of PsA pain (VAS 100 mm)
 - Patient's global assessment of disease activity (VAS 100 mm)
 - Physician's global assessment of disease activity (VAS 100 mm)
 - Patient self-assessed disability (Health Assessment Questionnaire [HAQ-DI©] score)
 - Acute phase reactant (C-reactive protein [hsCRP]) **or** Erythrocyte sedimentation rate (ESR).

In the definition above, the *baseline* value refers to the last measurement made prior to administration of the first dose of study treatment in core study.

The primary objective of this long term efficacy and safety study is to evaluate the proportion of subjects achieving ACR20, ACR50 and ACR70 by visit. Primarily, CRP will be used to calculate ACR response; ESR will only be used in the event CRP is missing.

ACR50 and ACR70 are defined in the same way as ACR20 by replacing the 20% with 50% and 70% improvement from baseline, respectively.

ACR_n represents the percent improvement on the continuous scale and from ACR_n one can directly calculate ACR20, ACR50, and ACR70 using the appropriate cutoffs. This variable is defined as:

$ACR_n = \min(x_1, x_2, x_3)$, where

x_1 = % improvement from baseline in tender 78-joint count

x_2 = % improvement from baseline in swollen 76-joint count

and x_3 = 3rd largest value of x_4, x_5, x_6, x_7, x_8 where,

x_4 = % improvement from baseline in Patient's assessment of PsA pain (VAS 100 mm)

x_5 = % improvement from baseline in Patient's global assessment of disease activity (VAS 100 mm)

x_6 = % improvement from baseline in Physician's global assessment of disease activity (VAS 100 mm)

x_7 = % improvement from baseline in Patient self-assessed disability (Health Assessment Questionnaire [HAQ©] score)

x_8 = % improvement from baseline in Acute phase reactant (C-reactive protein [hsCRP]) **or** Erythrocyte sedimentation rate (ESR)

ACR_n can be computed even if up to two values of x_4, x_5, x_6, x_7, x_8 are missing. ACR_n, theoretically, cannot be computed, if one or both of x_1, x_2 is/are missing OR more than three values of x_4, x_5, x_6, x_7, x_8 are missing.

Health Assessment Questionnaire - Disability Index (HAQ-DI)

The Health Assessment Questionnaire (HAQ[®]) was developed by Stanford University and is one of the most widely used measures to assess the long-term influence of chronic disease on a subject's level of functional ability and activity restriction. The disability assessment component of the HAQ (Health Assessment Questionnaire – Disability Index), the HAQ-DI, assesses a subject's level of functional ability and includes questions of fine movements of the upper extremity, locomotor activities of the lower extremity, and activities that involve both upper and lower extremities. There are 20 questions in eight categories of functioning including dressing, rising, eating, walking, hygiene, reach, grip, and usual activities. The stem of each item asks over the past week "Are you able to ..." perform a particular task. Each item is scored on a 4-point scale from 0 to 3, representing normal (normal, no difficulty [0]), some difficulty [1], much difficulty [2], and unable to do [3].

Scoring for the eight functional categories and overall disability index scoring will be performed as follows:

There are eight categories; first score within each category:

- Dressing and Grooming, includes items 1 and 2
- Arising, includes items 3 and 4
- Eating, includes items 5, 6 and 7
- Walking, includes items 8 and 9
- Hygiene, includes items 10, 11, and 12
- Reach, includes items 13 and 14
- Grip, includes items 15, 16 and 17
- Activities, includes items 18, 19, and 20

The score for each category will be the single response within the category with the highest score (greatest difficulty). For example, in the "Eating" category, there are two answers (one for each item). If "Cut your food with a knife or fork" is marked as "3" and "Lift a full cup or glass to your mouth" is marked as "0", then the score for the "Eating" category would be "3" (the response indicating the greatest difficulty within the category). If a component question is left blank or the response is too ambiguous to assign a score, then the score for that category will be determined by the remaining completed question(s). However, if **any** "aids or devices" and/or "help from another person" items at the bottom of each page are checked, the category to which they apply will be adjusted upward to "2". If the basic score is **already** "2" or "3", the score remains unchanged. "Aids or devices" and "help from another person" can **only** change a category's score to "2"; they do **not** change the score to a "1" or a "3".

The score for the disability index will be the mean of the eight category scores. If more than two of the categories, or 25%, are missing, scale will not be scored. Otherwise, divide the sum of the categories by the number of answered categories. The higher score indicates greater disability.

HAQ-DI response

The HAQ-DI response is defined by an improvement of at least 0.3 score points compared to baseline.

Joint/bone structural damage

The primary score for analyses will be van der Heijde modified Total Sharpe score (vdH-mTSS) (van der Heijde 1999), The erosion score and joint space narrowing score will be analyzed in similar fashion.

Erosions will be assessed each hand (20 locations per hand) and each foot (6 locations per foot). The maximum erosion score is 200 for all 40 hand locations, and 120 for all 12 feet locations. Thus, the total possible erosion score is 320.

Joint space narrowing (JSN) will be assessed in each hand (20 locations per hand) and foot (6 locations per foot). The maximum score is 160 for all 40 hand joints, and 48 for all 12 feet joints. Thus, the total possible JSN score is 208.

Pencil-in-cup: Osteolysis of the proximal phalanx and the base of the distal phalanx resulting in a pencil like proximal phalanx covered by cup like base of the distal phalanx. Pencil-in-cup will be scored as “P” where applicable.

Gross Osteolysis: Osteolysis of the phalanx resulting in a loss of the normal joint structure, usually accompanied by shortening of the length of the phalanx. Gross osteolysis will be scored as “G” where applicable.

If a joint or bone is not visible (e.g. poor film quality, missing imaging, severe misalignment, flexion deformity, dislocation) at the timepoint, the individual joint or bone will be coded as Not Visible (N).

If radiographs at the timepoint show a joint or bone with surgical fusion, replacement (prosthesis), or amputation, then the joint or bone will be scored Surgically Modified (S).

To obtain the total vdH-S score, scores for erosions and JSN in both the hands and feet will be added together. Any “P” or “G” will be considered the maximal score for the feature (erosions and JSN) per location in the calculation of the total vdH-S score. Any “N” or “S” will be considered null in the calculation of the total vdH-S score. The range of scores is 0 ~ 528.

The joints are divided into 10 segments according to [Table 12-1](#). In each segment an adequacy threshold is defined. For each segment, when the change from baseline values are available for at least the threshold number of joints, the change from baseline will be calculated for the segment, with missing joints imputed by the within-segment mean change over individual joints. Otherwise (i.e. if less than threshold number of joints have available change from baseline values), the segment change from baseline will be missing. When ≥ 6 segments have

[figure not shown]
evaluable change from baseline values, the overall change from baseline value will be calculated, with missing segments imputed by the mean change over segments. Otherwise (i.e. if ≤ 5 segments have evaluable change from baseline values), the overall change from baseline value will be missing.

[figure not shown]
[figure not shown]
Table 12-1 Segmental distribution

Segment	Total number of joints	Adequacy threshold	Joints at one side
PIP erosions	8	5	PIP2, PIP3, PIP4, PIP5
DIP erosions	8	5	DIP2, DIP3, DIP4, DIP5
MCP + thumb erosions	12	7	MCP1, MCP2, MCP3, MCP4, MCP5, INTERPHALANGEAL JOINT OF THE HAND
Wrist erosions	12	7	FIRST METACARPAL BONE, DISTAL RADIUS, DISTAL ULNA, TRAPEZOID-TRAPEZIUM, NAVICULAR BONE, LUNATE BONE
Foot erosions	12	7	MTP1, MTP2, MTP3, MTP4, MTP5, INTERPHALANGEAL JOINT 1
PIP JSN	8	5	PIP2, PIP3, PIP4, PIP5
DIP JSN	8	5	DIP2, DIP3, DIP4, DIP5
MCP + thumb JSN	12	7	MCP1, MCP2, MCP3, MCP4, MCP5, INTERPHALANGEAL JOINT OF THE HAND
Wrist JSN	12	7	CMC3, CMC4, CMC5, RADIOCARPAL, SCAPHOID-TRAPEZIUM, CAPITATE-NAVICULAR-LUNATE
Foot JSN	12	7	MTP1, MTP2, MTP3, MTP4, MTP5, INTERPHALANGEAL JOINT 1

The readings of the x-rays and the scoring will be performed centrally. Two central independent radiograph readers, both blinded to treatment arm and radiograph sequence, will analyze the digitized images. In the case that adjudication is needed, a third consensus read will be performed. The statistical analysis will use the adjudicated score, if available, or the average score from the two readers otherwise.

In the situation that a consensus is made, but not all joints are scored, the missing consensus score at an individual joint, both at baseline and post baseline, will be imputed with the average of the two individual readers' scores at the joint for the respective time point, then the consensus change from baseline (at patient level) is calculated based upon all individual joints with imputation at joint level.

DAS28, low disease activity and remission

The Disease Activity Score (DAS) is a combined index to measure the disease activity in patients with RA. 

The DAS28 is a measure of disease activity based on Swollen and Tender Joint Counts, CRP or ESR, and the Patient Global Assessment. A DAS28 score > 5.1 implies active disease, ≤ 3.2 low disease activity, and < 2.6 remission.

The following 28 joints will be assessed for tenderness and swelling: metacarpophalangeal IV (10), thumb interphalangeal (2), hand proximal interphalangeal II-V (8), wrist (2), elbow(2), shoulders (2), and knees (2).

The following formulas can be used to calculate the DAS28 with CRP (mg/L) or ESR (mm/hour).

$$\text{DAS28-CRP} = 0.56 \cdot \sqrt{\text{TJC28}} + 0.28 \cdot \sqrt{\text{SJC28}} + 0.36 \cdot \ln(\text{CRP}+1) + 0.014 \cdot \text{PGA} + 0.96$$

[figure not shown]
$$\text{DAS28-ESR} = 0.56 \cdot \sqrt{\text{tender28}} + 0.28 \cdot \sqrt{\text{swollen28}} + 0.70 \cdot \ln(\text{ESR}) + 0.014 \cdot \text{PGA}$$

TJC28: 28 Tender joint count; SJC28: 28 Swollen joint count; CRP: C-reactive protein; PGA: Patient Global Assessment

If any component measurement is missing, DAS28 will be missing.

DAS28-CRP will be primary for analysis; DAS-ESR will be secondary.

DAS28-CRP (or ESR) remission is defined as a DAS28-CRP (or ESR) index score less than 2.6. Low disease activity is defined as DAS28-CRP (or ESR) index less than or equal to 3.2.

ACR Components

Tender 78 joint count and swollen 76 joint count

The 78 joints assessed for tenderness include the 2 temporomandibular, 2 sternoclavicular, 2 acromioclavicular joints, 2 shoulders, 2 elbows, 2 wrists, 2 first carpometacarpal, 10 metacarpophalangeal, 10 proximal interphalangeal, 8 distal interphalangeal joints of the hands, the 2 hip, 2 knee, 2 talo-tibial, 2 mid-tarsal, 10 metatarsophalangeal, 10 proximal interphalangeal, and 8 distal interphalangeal joints of the feet. All of these except for the hips are assessed for swelling. Joint tenderness and swelling are to be graded present (1) or absent (0). Synovial fluid and/or soft tissue swelling but not bony overgrowth represents a positive result for swollen joint count. Dactylitis of a digit in the foot or hand counts as one tender and swollen joint.

If the number of joints for which data were available (e.g., T) is less than 78/76 for the tender/swollen joint assessment, the number of tender/swollen joints (e.g., t) will be scaled up proportionately (i.e., $78*t/T$ or $76*t/T$ for tender or swollen joint count).

Patient's assessment of PsA Pain

The patient's assessment of pain will be performed using 100 mm visual analog scale (VAS) ranging from "no pain" to "unbearable pain" after the question "*Please indicate with a vertical mark (|) through the horizontal line the most pain you had from your psoriatic arthritis today*".

Patient's global assessment of PsA disease activity

The patient's global assessment of disease activity will be performed using 100 mm VAS ranging from "very good" to "very poor", after the question "*Considering all the ways psoriatic arthritis affects you, please indicate with a vertical mark (|) through the horizontal line how well you are doing today*".

Physician's global assessment of PsA disease activity

[figure not shown]
The physician's global assessment of disease activity will be performed using 100 mm VAS ranging from no disease activity to maximal disease activity, after the question "*Considering all the ways the disease affects your patient, draw a line on the scale for how well his or her condition is today*". To enhance objectivity, the physician must not be aware of the specific patient's global assessment of disease activity, when performing his own assessment on that patient.

[figure not shown]
Erythrocyte sedimentation rate (ESR)

[figure not shown]
Blood for ESR, which is helpful in diagnosing inflammatory diseases and is used to monitor disease activity and response to therapy, will be obtained at scheduled visits.

[figure not shown]
[figure not shown]
High-sensitivity C-reactive protein (hsCRP)

[figure not shown]
Blood for this assessment will be obtained in order to identify the presence of inflammation, to determine its severity, and to monitor response to treatment. Since the results of this test may unblind study personnel, results from the central lab will be provided for screening and baseline only. The hsCRP results from samples collected during the treatment period will be revealed following database lock only.

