13.9 Appendix 9: Health Assessment Questionnaire (HAQ)[®]

The HAQ[®] (Fries JF et al. 1980) is a validated measure of physical disability and functional status. It has four dimensions: disability, pain, drug side effects and dollar costs, although, the latter three are rarely used in clinical trials. In this trial only the disability dimension will be used. The disability dimension consists of 20 multiple choice items concerning difficulty in performing eight common activities of daily living; dressing and grooming, arising, eating, walking, reaching, personal hygiene, gripping and activities. Patients choose from four response categories, ranging from 'without any difficulty' to 'unable to do'. The ACR Rheumatology Committee on Outcome Measures in RA recommends the use of this questionnaire in clinical trials.

Scoring of the HAQ[®]

The HAQ[®] will be scored in accordance with the recommendation from the developers outlined in the "HAQ PACK" from Stanford University, California.

The following coding is to be used for the 8 categories of the disability outcome dimension:

Without ANY Difficulty	0
With SOME Difficulty	1
With MUCH Difficulty	2
UNABLE to do	3

Within each of the 8 categories only the item indicating the most severe impairment contributes to the category score. If the patient requires the use of aids, devices, or help from another to accomplish any of the activities in an associated category, then the score for that category will be assigned the value 2, unless the score is already 3 (i.e. scores of 0 or 1 are increased to 2). Associated categories are defined in the "HAQ PACK". From the scores for each category a Standard Disability Index (SDI) is computed by summing the computed scores for each category and dividing by the number of categories answered. The SDI is not computed if the patient does not have scores for at least 6 categories. This SDI is the HAQ[®] score, which will be used in the statistical analyses of this instrument. The range for this score is (0, 3).

HAQ[®] Data Collection

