Extension Full analysis set (extension FAS): The extension FAS will be comprised of all subjects enrolled in the extension study and have at least one post baseline assessment of efficacy during the extension period. Subjects will be analyzed according to the treatment assigned to.

(In this document extension FAS is referred as to FAS).

Of note, FAS will comprise only the subjects from extension whereas safety set will include from core or extension, safety set will be larger than FAS.

Up-titration Subset: The up-titration subset will be comprised of subjects from the extension FAS set who received at least one dose of the up-titration dose.

Psoriasis subset: The psoriasis subset will include all FAS subject who have $\geq 3\%$ of the body surface area (BSA) affected by psoriatic skin involvement at baseline.

Nail subset: The nail subset will include all FAS subject who have psoriasis currently in nails at baseline.

Safety set: The safety set includes all subjects who took at least one dose of study treatment during the treatment period in core or extension study. Subjects will be evaluated according to treatment received.

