5.1 Treatment groups

The arms included in efficacy tables are based on the treatment sequence (picturing also the up-titration) for the periods up to the final lock at week 260. Two separate columns will display the assigned and actual treatment resulting in the following treatment sequences:

Efficacy:

- AIN457 10 mg/kg - 75 mg
- AIN457 10 mg/kg - 75 mg - 150 mg
- AIN457 10 mg/kg - 75 mg - 300 mg
- AIN457 10 mg/kg - 150 mg
- Placebo - AIN457 75 mg
- Placebo - AIN457 75 mg - 150 mg
- Placebo - AIN457 75 mg - 300 mg
- Placebo - AIN457 150 mg

After week 52 the combination of assigned treatment will also be shown.

- AIN457 75 mg & Placebo - AIN457 75 mg
- AIN457 150 mg & Placebo - AIN457 150 mg

The treatment sequence following up-titration for the combined groups will be:

- AIN457 75 mg & Placebo - AIN457 75 mg - 150 mg
- AIN457 75 mg & Placebo - AIN457 75 mg - 300 mg
- AIN457 150 mg & Placebo - AIN457 150 mg – 300 mg

Cases might up-titrate twice; for these cases the treatment prior to each up-titration will be displayed (that is not the assigned treatment for the 2nd observed up-titration). Therefore, at the graphical representation of up-titration the actual treatment dose prior to the switch will be displayed.

Regarding safety, the arms included in the entire treatment period are as follows.

- Any AIN457 75 mg
- Any AIN457 150 mg
- Any AIN457 300 mg
- Any AIN457 (if appropriate)

Placebo group will be included at the in-text tables and listings of the CSR.

In the safety listings the groups will be the following:

- AIN457 10 mg/kg - 75 mg
- AIN457 10 mg/kg - 150 mg
- Placebo AIN457 75 mg
- Placebo AIN457 150 mg
- Placebo not re-randomized.

6 Subgroup definitions

The primary endpoint and secondary endpoints will be evaluated for TNF-alpha inhibitor status and by concomitant MTX use (ACR20/50, [REDACTED]).

7 Assessment windows, baseline and post baseline definitions, missing data handling

Baseline and post-baseline definitions

In general, a *baseline* value refers to the core study and is the last measurement made prior to administration of the first dose of study treatment in core. Baseline information will be presented appropriately in the “by visit” summaries in both safety and efficacy tables.

A post-baseline value refers to a measurement taken after the first dose of study treatment in core study.

Analysis visit windows

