12.4 Analysis of Primary Variable(s)

The primary efficacy variable(s) is the clinical response to treatment according to ACR20, ACR50 and ACR 70 improvement in disease activity over time up to Week 260.

ACR response criteria denote the response (i.e., improvement) in signs & symptoms of the disease of a subject compared to baseline of the core study.

The analysis of the primary variables will be based on the FAS. Primarily, CRP will be used instead of ESR to calculate ACR response; ESR will only be used in the event CRP is missing.

Shift tables will be provided comparing the subject's ACR evaluation at the pre up-titration visit relative to the observed data of the following week intervals after up-titration: (12-32 weeks), (36-56 weeks) and (60-80 weeks). The ACR grouping presented in the table will be: $ACR < 20$, $20 \leq ACR < 50$, $50 \leq ACR < 70$, $ACR \geq 70$.

Graphical representation (line plots) of ACR20, ACR50 and ACR70 response over time and Sankey-style bar chart for the ACR response within the subjects that up-titrated from 150 mg to 300 mg (provided that up-titration has been occurred for more than 8 weeks) will be drawn from the observed data.

Additionally, observed data tables will summarize the ACR20, ACR50 and ACR70 response following up-titration when assessed. Results will be illustrated in line plots.

Also individual subject listings of the ACR components as well as for the ACR20/50/70 response will be given.

Statistical model, hypothesis, and method of analysis

No formal hypotheses are planned for this study. The proportion of subjects meeting the ACR criteria (ACR20, ACR50, and ACR70) will be descriptively summarized for each treatment by absolute and relative frequencies followed by 95% confidence intervals for the proportion of patients responding to treatment according to the ACR criteria from Week 1 onwards based on the pooled data from core and extension study. Results regarding ACR20/50/70, will be presented overall in the FAS population as well as in subgroups by TNF α status (naive or IR) and by concomitant use of MTX as appropriately.

Placebo group (core study) in efficacy analysis will not be considered.

All the above efficacy variables will be analyzed on the FAS (unless otherwise specified) for all applicable analysis visits based on the observed data.

For binary variables, the proportion of responders along with the 95% CI will be presented by treatment groups over analysis visits.

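### HAQ-DI response (improvement of at least 0.3) is reported on all FAS subjects, although those with a core baseline below 0.3 cannot respond; the plan should also show the proportion among subjects able to respond

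*SAP*

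**What the plan says.** HAQ-DI response serves secondary objective 1b, the proportion of subjects whose HAQ-DI improvement reaches the minimal clinically important difference (Protocol 2.2; SAP 3.2). SAP 12.1 sets the cut: "The HAQ-DI response is defined by an improvement of at least 0.3 score points compared to baseline".

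On scoring, SAP 12.1 says: "The score for the disability index will be the mean of the eight category scores". When one or two categories are missing: "Otherwise, divide the sum of the categories by the number of answered categories". Each category scores 0 to 3, and Protocol Appendix 9 gives the index a range of 0 to 3.

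On baseline, SAP Section 7 says it "is the last measurement made prior to administration of the first dose of study treatment in core". One fixed pre-dose value therefore serves every visit up to Week 260.

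On the denominator, SAP 12.4 says: "All the above efficacy variables will be analyzed on the FAS (unless otherwise specified) for all applicable analysis visits based on the observed data". It adds: "For binary variables, the proportion of responders along with the 95% CI will be presented by treatment groups over analysis visits". The FAS definition in SAP Section 5 has no condition on baseline HAQ-DI. The same section does define baseline-restricted subsets for skin and nails; the first begins "The psoriasis subset will include all FAS subject who have" and requires at least 3% body surface area involved at baseline. There is no such subset for HAQ-DI.

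SAP 12.4 plans HAQ-DI response figures overall, following up-titration and by TNF-alpha inhibitor status.

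**The concern.** A responder definition based on an absolute drop has a floor when the scale ends at 0. A subject who starts at 0.25 and scores 0 at every later assessment has the best function the instrument can record, yet is scored as a non-responder each time. The reported proportion then combines two things: how often subjects with room to improve do so, and how many subjects had no such room.

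The second component can differ between columns. The up-titration columns are formed by the investigator's judgement of incomplete control (Protocol 3.1), not by randomisation, and the TNF-alpha subgroups are patient characteristics. If the low-baseline share differs between such groups, part of any visible difference in HAQ-DI response comes from the floor. As planned, nothing beside the proportion tells the reader how large that part is.

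**Working it through.** The plan states no expected HAQ-DI response rate, sample size or power for this endpoint, so there is no figure to reproduce. The check has two parts.

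**1. Which baselines cannot respond.** With k answered categories, the attainable scores are i/k for i = 0, …, 3k. The best later score is 0, so the largest possible improvement equals the baseline. Response is impossible when baseline < 0.3.

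| Categories answered at baseline | Step | Baselines that cannot respond | Lowest baseline that can |
|---|---|---|---|
| 8 | 1/8 = 0.125 | 0, 0.125, 0.25 | 3/8 = 0.375 |
| 7 | 1/7 | 0, 1/7 (0.143), 2/7 (0.286) | 3/7 (0.429) |
| 6 | 1/6 | 0, 1/6 (0.167) | 2/6 (0.333) |

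With all eight categories answered at both visits, the 0.3 cut works as 0.375 (three steps). A subject at 0.375 responds only by reaching exactly 0.

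**2. Effect on the reported proportion.** Let f be the share of subjects in a column, with an observed score at the visit, whose core baseline is below 0.3. Let r be the response rate among the rest. Then

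- all-FAS rate = (1 − f) × r + f × 0 = (1 − f) × r
- gap relative to r = f × r

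The documents give neither f nor r. The values below are assumptions.

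| f (assumed) | r (assumed) | All-FAS rate | Gap, points |
|---|---|---|---|
| 5% | 60% | 0.95 × 60 = 57.0% | 3.0 |
| 8% | 60% | 0.92 × 60 = 55.2% | 4.8 |
| 12% | 60% | 0.88 × 60 = 52.8% | 7.2 |
| 5% | 50% | 0.95 × 50 = 47.5% | 2.5 |
| 10% | 50% | 0.90 × 50 = 45.0% | 5.0 |

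Over a wider range, f = 2% with r = 40% gives 0.8 points, and f = 20% with r = 70% gives 14 points. For scale, 5% and 12% of the 460 enrolled subjects (Protocol Section 4) are about 23 and 55 people.

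**Between columns.** If r is the same in two columns and f differs by 5 points, the floor alone produces a difference of 0.50 × 5 = 2.5 points at r = 50%, or 0.60 × 5 = 3 points at r = 60%.

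**The case against.** The strongest reply is that the SAP does what the objective asks. Objective 1b is a proportion of subjects, with no baseline condition. A subject who moves from 0.25 to 0 did not improve by the stated difference, so calling that subject a non-responder is literally correct. This stands. A reader might infer that the all-FAS proportion is an error to be replaced, and the documents do not support that. The restricted proportion answers a different, complementary question.

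A reader might also infer from the absence of a HAQ-DI minimum in the extension's eligibility criteria that many low-baseline subjects are present. That does not follow. Baseline is the core value, the core eligibility criteria are not in the documents (Protocol Appendix 11 gives only the core design), and extension criteria say nothing about how many subjects started below 0.3.

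Nor are these subjects counted as failures at every scheduled visit. SAP 12.3 uses observed data, so a missing visit leaves the denominator.

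Other points carry partial weight:

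- Change from baseline in HAQ-DI is objective 1a and is plotted, baseline HAQ-DI is summarised (SAP 8.2) with minimum and lower quartile (SAP Section 4), and listings are planned. A large low-baseline share would leave traces, but none of these gives the number unable to respond next to each proportion.
- No formal hypotheses are planned, and Protocol 9.5.1 excludes treatment comparisons for secondary variables. The original arms were randomised and stratified by TNF status, so f was balanced in expectation between them at core randomisation. The up-titration columns lack that protection, though their differences could not be read as drug effect in any case.
- With an assumed 230 subjects per dose (460/2), the 95% half-width near 57% is 1.96 × √(0.57 × 0.43/230), about 6 points, so a gap of 2.5 to 3 points between columns is smaller than the sampling error.
- The skin and nail subsets are a loose analogy. They require the manifestation to be present, whereas HAQ-DI is defined for everyone. They show only that the SAP accepts baseline-restricted denominators where they suit the measure.

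**Conclusion.** The structural point holds from the SAP's own scoring and response rules: a core baseline below 0.3 rules out response, and such subjects count as non-responders at each visit with an observed score. No readable passage limits the denominator. Some SAP text is redacted, but the analysis-set definitions are legible and contain no such limit.

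The size is unknown. The all-FAS rate lies f × r below the rate among those able to respond, about 3 to 7 points for f = 5% to 12% and r = 60%, all assumed. It would be negligible if few subjects started that low. No alpha or power is involved, since the endpoint is secondary and descriptive. The effect is on how the proportion and its interval are read, chiefly in the up-titration columns and TNF-alpha subgroups.

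This is an inexpensive improvement in reporting, not the correction of a wrong analysis.

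**What to change.** In SAP 12.4, for HAQ-DI response overall, following up-titration and by TNF-alpha inhibitor status:

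1. Keep the all-FAS proportion with its 95% CI, as the result that matches objective 1b.
2. Add a row with the proportion and 95% CI among FAS subjects whose core-baseline HAQ-DI is at least 0.3.
3. Show, in each column, the number of subjects with core baseline below 0.3.

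State the condition on the score itself (below 0.3), not as a list of values, so that scores built from six or seven categories are covered.

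The data come from the core study and sit in the same database (Protocol 6.2), so conduct is unaffected. The cost is one extra row on a smaller denominator. At a fixed proportion the interval widens by roughly 1/√(1 − f), a factor of about 1.03 at f = 5% and 1.07 at f = 12%. The added row does not remove all floor effects, because subjects just above the cut still have little room to improve.
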